10.3.2 Demographic, Medical History, Prior Medication and other Baseline Characteristics

Demographic characteristics, medical history, prior medication and other baseline data will be listed and summarized using descriptive statistics for numerical data and contingency tables for categorical data. Medical history and prior medication will only be listed.

10.3.3 Study vaccine

The administrations of CV7202 will be listed.

10.3.4 Concomitant medication and Vaccinations

Concomitant medication/vaccination and significant non-drug therapies after the start of study treatment will be listed and summarized by Anatomical Therapeutic Chemical (ATC) term in contingency tables.

10.3.5 Safety Analyses

The following safety and reactogenicity data will be summarized descriptively: vital signs, and vaccination site reactogenicity assessment.

The occurrence of solicited local and systemic AEs reported on the day of each vaccination and the 7 subsequent days and unsolicited AEs reported on the day of each vaccination and the 28 subsequent days will be presented.

The safety measurements will include:

1. AEs (type, intensity, frequency and relationship to vaccination), i.e. incidence and severity of AEs for both solicited local and systemic events (occurring on the day of vaccination and the 7 subsequent days) and unsolicited events (occurring on the day of vaccination and the 28 subsequent days).
2. SAEs, MAAEs and AEs leading to trial or vaccine withdrawal up to 12 months post last dose. After Visit 15 (Month 12), only SAEs and MAAEs that according to the

investigator are considered to be related to study vaccination will be collected.

3. Intercurrent medical conditions and AESIs throughout the trial.
4. Local reactogenicity assessment of injection site in all subjects.

Further, the incidence of AEs will be summarized in frequency tables by Medical Dictionary for Regulatory Activities (MedDRA) terms (system organ class [SOC] and preferred term [PT]). AEs that are reported as related to the test vaccine will be considered trial vaccine-related; missing classifications concerning trial vaccine relationship will also be considered trial vaccine-related.

Concomitant medications and vaccinations will be coded and summarized. Physical examination data will be listed.

Clinical laboratory test results with values below/above the reference range will be counted.

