| | 3 | Significant; any use of narcotic pain reliever and/or prevents daily activity |
| Fatigue | 0 | Absent |
| | 1 | Mild, no interference with normal activity |
| | 2 | Moderate, some interference with normal activity |
| | 3 | Significant, prevents normal activity |
| Chills | 0 | Absent |
| | 1 | Mild, no interference with normal activity |
| | 2 | Moderate, some interference with normal activity |
| | 3 | Severe, prevents normal activity |
| Myalgia | 0 | Absent |
| | 1 | Mild, no interference with normal activity |
| | 2 | Moderate, some interference with normal activity |
| | 3 | Significant, prevents normal activity |
| Arthralgia | 0 | Absent |
| | 1 | Mild, no interference with normal activity |
| | 2 | Moderate, some interference with normal activity |
| | 3 | Significant, prevents normal activity |
| Nausea/ Vomiting | 0 | Absent |
| | 1 | Mild, no interference with activity and/or 1 – 2 episodes/ 24 hours |
| | 2 | Moderate, some interference with activity and/or >2 episodes/ 24 hours |
| | 3 | Severe, prevents daily activity, requires outpatient i.v. hydration |
| Diarrhea | 0 | Absent |
| | 1 | 2 – 3 loose stools or <400 g/24 hours |
| | 2 | 4 – 5 stools or 400 – 800 g/24 hours |
| | 3 | 6 or more watery stools or >800 g/24 hours or requires outpatient IV hydration |

*FDA toxicity grading scale [25]; i.v. = Intravenous.

Laboratory data will be graded according with the FDA toxicity grading scale [25] and the Common Terminology Criteria for Adverse Events (CTCAE) Version 5.0 [26]. These guidelines however are dependent upon institutional normal parameters. Institutional normal reference ranges should be provided to demonstrate that they are appropriate.

AEs with a suspected immune mediated disease etiology will be considered AESIs. The list of AESI is provided in (Appendix 10).

Definitions and Procedures for Recording, Evaluating, Follow-up, and Reporting of AEs are provided in Appendix 11.

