| 
• Any abnormal laboratory test results (hematology, clinical chemistry, or urinalysis) or other safety assessments (e.g., ECG, radiological scans, vital signs measurements), including those that worsen from baseline, considered clinically significant in the medical and scientific judgment of the investigator (i.e., not related to a known concomitant disease).• Exacerbation of a pre-existing condition including either an increase in frequency and/or intensity of the condition.• New conditions detected or diagnosed after trial vaccine administration even though it may have been present before the start of the trial.• Signs, symptoms, or the clinical sequelae of a suspected drug-drug interaction.• Signs, symptoms, or the clinical sequelae of a suspected overdose of either trial vaccine, including Rabipur® or a concomitant medication/vaccination.• An adverse effect of the trial vaccine, including Rabipur® or concomitant medication/vaccination.• An accident or injury. |
| Events NOT Meeting the AE Definition |
| 
• Surgical procedures or other therapeutic interventions themselves are not AEs, but the condition for which the surgery/intervention is required is an AE and should be documented accordingly.• Planned surgical measures and the condition(s) leading to these measures are not AEs, if the condition(s) was (were) known before the period of observation (see below) and did not worsen during study. In the latter case the condition should be reported as medical history.• Situations in which an untoward medical occurrence did not occur (social and/or convenience admission to a hospital). |

- Anticipated day-to-day fluctuations of pre-existing disease(s) or condition(s) present or detected at the start of the trial that do not worsen.

Definition of an SAE

If an event is not an AE per definition above, then it cannot be an SAE even if serious conditions are met.

An SAE is defined as any untoward medical occurrence that, at any dose:

- Results in death.

- Is life-threatening.

The term 'life-threatening' in the definition of 'serious' refers to an event in which the subject was at risk of death at the time of the event. It does not refer to an event, which hypothetically might have caused death, if it were more severe.

- Requires inpatient hospitalization or prolongation of existing hospitalization:

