- Overall summary of unsolicited AEs that contain an overview of each item below
- All AEs
 - Mild (grade 1) AEs
 - Moderate (grade 2) AEs
 - Severe (grade 3) AEs
- Related AEs
 - Mild (grade 1) related AEs
 - Moderate (grade 2) related AEs
 - Severe (grade 3) related AEs
- SAEs
- Related SAEs
- MAAEs
- AEs leading to withdrawal from study
- AEs leading to discontinued vaccination

- AESIs

Laboratory data will be graded by the site in the AE form according to the United States Food and Drug Administration toxicity grading scale and the Common Terminology Criteria for Adverse Events Version 5.0.

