11.7 Safety Laboratory Evaluation

Laboratory parameters (hematology, biochemistry, and coagulation) will be summarized using descriptive statistics at baseline and at each postbaseline time point. The categorization into low-normal-high (below lower reference range/ within reference range/ above upper reference range) will also be summarized. In summary tables, results below or above the detection limit are set to the detection limit.

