14.3.7.3.1 Hematology, Safety Analysis Set

Parameter (unit)	CV7202 1 µg (N = xx)	CV7202 2 µg (N = xx)	CV7202 5 µg (N = xx)	Rabipur (N = xx)
Parameter (unit)	Visit xx			
n	xx	xx	xx	xx
Mean (SD)	xx.x (xx.xx)	xx.x (xx.xx)	xx.x (xx.xx)	xx.x (xx.xx)
Median	xx.x	xx.x	xx.x	xx.x
Min, Max	xx, xx	xx, xx	xx, xx	xx, xx
Low	xx (xx.x%)	xx (xx.x%)	xx (xx.x%)	xx (xx.x%)
Normal	xx (xx.x%)	xx (xx.x%)	xx (xx.x%)	xx (xx.x%)
High	xx (xx.x%)	xx (xx.x%)	xx (xx.x%)	xx (xx.x%)
Visit xx	...			

Values are categorized into low-normal-high (below lower reference range/ within reference range/ above upper reference range). In the occurrence of a repeat, only the last valid result is considered.

Unscheduled visits are not presented for this summary. Results reported as below or above the detection limit are set to the detection limit.

PROGRAM SOURCE: tlf-###, DATA CUT OFF DATE: DDMMYYYY

RUN DATE: DDMMYYYY hh:mm

Programming note:

Display for all hematology parameters and all visits and timepoints with data collected for these parameters.

Number of decimals will vary by parameter - in general present mean, median to 1 decimal more than individual data, SD to 2 decimals more than individual data. Refer to SAP.

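### Laboratory results get a toxicity grade only if reported as adverse events, and no laboratory output shows a shift or change from baseline or a split by dose regimen, although Protocol 9.1 says laboratory data will be graded

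*Protocol*

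**What the plan says.** **Protocol.** Section 10.3.5 gives the laboratory analysis in one sentence: "Clinical laboratory test results with values below/above the reference range will be counted". Section 9.1 states: "Laboratory data will be graded according with the FDA toxicity grading scale [25] and the Common Terminology Criteria for Adverse Events" (version 5.0). Two scales are named, with no rule for which applies to which parameter.

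**SAP tables.** Section 11.7 goes further than Protocol 10.3.5: "Laboratory parameters (hematology, biochemistry, and coagulation) will be summarized using descriptive statistics at baseline and at each postbaseline time point". It adds: "The categorization into low-normal-high (below lower reference range/ within reference range/ above upper reference range) will also be summarized". Shells 14.3.7.3.1 to 14.3.7.3.3 show n, mean, SD, median, minimum, maximum and the three categories for each parameter and visit. The columns are 1 µg, 2 µg, 5 µg and Rabipur. SAP Appendix C lists no version of these tables by dose regimen, although it lists one for VNTs, immunoglobulins, cytokines and injection-site assessments.

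**Grading.** SAP 11.2.2 says: "Laboratory data will be graded by the site in the AE form". Under Protocol Appendix 11, an abnormal laboratory result is an AE when it is "considered clinically significant in the medical and scientific judgment of the investigator". The trial is open label (Protocol 8.6).

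**Listings.** Output 14.3.4 lists abnormal values by subject. Listings 16.2.8.1 to 16.2.8.3 give value, limits, high/low and the investigator's clinical-significance assessment, with no grade and no change column. By contrast, the vital signs listing (16.2.9.2) has a change column, and SAP 10.3.2 and 10.3.3 plan change-from-baseline summaries for cellular and cytokine data.

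**Declared changes.** SAP 12 mentions only the dropped per-protocol sets.

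**The concern.** Safety is the primary objective of this first-in-human trial. For laboratory data the basic question is how many subjects, at each dose level and after each dose, had an abnormality that was new or worse than before vaccination, and how bad it was. The planned tables do not answer it, for four reasons:

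- A grade exists only for results that an investigator who knows the vaccine given has chosen to report as an AE.
- The low/normal/high rows count a marginal value and an extreme one alike.
- Entry requires no clinically significant laboratory findings (inclusion criterion 3), not values within range. A stable value out of range before vaccination can therefore be counted again at each later visit.
- After the second dose on Day 29, the 1 µg and 2 µg columns mix subjects who had one dose with subjects who had two.

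**Working it through.** **1. Visits.** Protocol 9.5.1 gives 12 safety-laboratory visits: V2 to V5, V7 to V10 and V12 to V15. At 9 ml each, 12 × 9 = 108 ml, which matches Table 9.3. Two visits (V2, and V3 before dosing) precede vaccination, which leaves 10. V9 is held only for Group 1 and Groups 3a and 4a (Protocol 9.4.10), so one-dose subjects have 9. A value that stays out of range from before vaccination thus adds 9 or 10 flags to the post-dose tables, none of them new.

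**2. Chance flags per subject.** The documents give no such figure, so this rests on assumptions.

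- Biochemistry: 15 parameters (counted from Table 12.1).
- Haematology: H is not stated; assumed 5 to 14.
- Coagulation: 2 parameters, at C visits. C is 4 in all, 2 post-dose for two-dose and Rabipur subjects, and 1 for one-dose subjects.
- Chance rate r of an out-of-range result: not stated; assumed 5%, or 2.5% for one-sided ranges.

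Expected flags = [(15 + H) × visits + 2 × C] × r.

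- One-dose, H = 5, r = 2.5%: (20 × 9 + 2) × 0.025 = 182 × 0.025 = 4.6
- One-dose, H = 10, r = 5%: (25 × 9 + 2) × 0.05 = 227 × 0.05 = 11.4
- Two-dose or Rabipur, H = 14, r = 5%: (29 × 10 + 4) × 0.05 = 294 × 0.05 = 14.7
- All 12 visits, H = 14, r = 5%: (29 × 12 + 8) × 0.05 = 356 × 0.05 = 17.8

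The range is about 5 to 18. Its top includes the two pre-vaccination visits; counting post-dose visits only, it is about 5 to 15.

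**3. What the counts can show for a whole group.** These flags spread over many parameter-by-visit cells, so the expected chance count per cell is small: 16 × 0.05 = 0.8, or 10 × 0.05 = 0.5. Exact binomial tails, assuming independent subjects:

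| Count in one cell | 5% (chance) | 30% affected | 50% affected |
|---|---|---|---|
| 4 or more of 16 | 0.7% | 75.4% | 98.9% |
| 3 or more of 10 | 1.1% | 61.7% | 94.5% |

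With H = 7 there are 22 × 10 + 4 = 224 cells per group. Chance alone then gives 224 × 0.0070 = 1.6 cells with 4 or more of 16. A large effect across a group stands out; a 30% effect does so less reliably.

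**4. Second-dose effect.** Suppose half of the eight two-dose subjects are affected and the eight one-dose subjects flag at 5%. The pooled column reaches 4 or more of 16 with probability 71.7%. In a separate column of eight, 3 or more has probability 85.5%, against 0.6% by chance. At a similar chance rate, the dose-regimen split detects more.

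**5. One or two severe changes.** At 5%, the chance of at least one flag in a cell is 34%, 40% and 56% for 8, 10 and 16 subjects. For at least two it is 5.7%, 8.6% and 18.9%. A severe change in one or two subjects is therefore an ordinary-looking count. Minimum and maximum show the extreme value, but not how many subjects were affected or where they started.

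**The case against.** The strongest reply has four parts.

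- **The SAP plans much more than counts.** True. A reader of Protocol 10.3.5 alone might infer that laboratory safety is reduced to out-of-range counts. SAP 11.7, output 14.3.4 and listings 16.2.8.1 to 16.2.8.3 show otherwise.
- **The grading sentence stands under the heading Adverse Events, and the SAP carries it out through the AE form.** This reading is defensible, and graded laboratory AEs do enter the maximum-intensity AE tables. But the Protocol sentence is not limited to reported AEs, and either reading leaves the tables without a within-subject comparison.
- **With 53 vaccinated subjects the listings can be read by eye.** Partly true: a subject's values sit together within each parameter. By SAP 6.4, however, there are 26 one-dose subjects (10 + 8 + 8) and 27 with two CV7202 doses or Rabipur (8 + 8 + 11), if each got the planned regimen. With H = 7 they produce 26 × 200 + 27 × 224 = 11,248 post-dose results, of which 5%, about 562, would be out of range by chance. A reader would have to grade and pair them by hand.
- **Laboratory values are neither a primary nor a secondary endpoint, and the trial is descriptive.** This stands and limits the weight of the point.

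Two stronger inferences fail. One is that chance flags would hide any real change; step 3 shows that a large group-wide effect remains visible. The other is that dose decisions suffered. DSMB review follows its own charter (Protocol 5.5). The SAP is dated 24 February 2022 and reports that all 53 subjects had already been vaccinated, so these report tables did not guide escalation.

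**Conclusion.** The gap is real but moderate. Grading is confined to laboratory findings reported as AEs, and no output provides a programmed grade, a within-subject shift or a change from baseline. The tables therefore cannot state how many subjects had a new or worsened abnormality after vaccination, or its severity.

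Large effects across a whole group would be seen (98.9% for half of 16). Weaker effects (75.4% for 30% of 16), second-dose effects in the pooled column (71.7%) and severe changes in one or two subjects are poorly separated from trivial flags. These figures assume a 5% chance rate and independent subjects. The 5 to 18 chance flags per subject also depend on the assumed number of haematology parameters. Selection at entry would lower them; correlation within a subject would cluster them without changing the mean.

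**What to change.** In Protocol 10.3.5 and SAP 11.7:

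- Derive a toxicity grade by program for every gradable numeric result, with one of the two named scales fixed for each parameter.
- Tabulate each subject's worst post-dose grade against the baseline grade, by vaccination group and dose regimen and after each dose. Use the SAP 6.1 baseline, the last non-missing value before the first dose.
- For parameters without a grade, tabulate the low/normal/high shift in the same way.
- Keep the by-visit tables and the listings.

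The cost is modest programming, a few more tables and the choice of one scale per parameter; no new data are needed. One limitation is that the worst category over many visits has its own chance rate. At 5% per visit, with independent visits, it is 1 − 0.95^9 = 37% for one ungraded parameter over nine visits, and less if visits are positively correlated. That is a reason to prefer grades where they exist and to keep the by-visit display. If the tables are added after SAP finalization, label them post hoc, as SAP 6 requires.

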10.3.6 Immunogenicity Analyses (Secondary/Exploratory Objectives)

Baseline is defined as Day 1 (Visit 3; before vaccination).

Immune response will be assessed using the following parameters:

1. Number and percentage of subjects having VNTs ≥ 0.5 IU/ml on Days 1, 15, 43, and 12, 18 and 24 months post last dose.
2. Individual functional antibody titers, GMTs and range of titers in sera collected on Days 1, 8, 15, 29, 36, 43, 57, 91, and 6, 12, 18 and 24 months post-last dose.

Further immunogenicity assessments will be based on VNTs, RABV-G-specific IgG, IgM and IgA serum antibodies, RABV-G-specific T cells and B cells in peripheral blood and other immunogenicity-related parameters such as cytokine serum concentrations, including but not limited to CXCL10, CCL3, IL-6, TNF - α and IFN- γ , gene expression changes, antibody affinity and avidity, throughout the duration of the trial. Results will be summarized in tables, figures and supported by subject level listings.

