| Table 2.2 | Staggered Enrolment and Dose Escalation for Groups 2 to 4 (Dose 1) with Minimum Time Intervals* | 16 |
| Table 8.1 | Protocol CV-7202-104 Dose regimen | 37 |
| Table 9.1 | Intensity Grading for Solicited Local AEs (Days 1 to 8) | 39 |
| Table 9.2 | Intensity Grading* for Solicited Systemic AEs (Days 1 to 8) | 40 |
| Table 9.3 | Timing and Maximum Volumes of Blood Draws | 54 |
| Table 12.1 | Protocol-Required Safety Laboratory Assessments | 73 |
| Table 12.2 | List of Names and Addresses | 74 |

List of Figures

| | | |
|------------|--------------------------------|----|
| Figure 5.1 | CV-7202-104 Trial Design | 23 |
|------------|--------------------------------|----|

1 Synopsis

| | |
|---|--|
| Protocol Title: | A non-randomized, open label, controlled, dose-escalation, phase I clinical trial to evaluate the safety, reactogenicity and immunogenicity of one or two administrations of candidate rabies mRNA vaccine CV7202 in healthy adult subjects |
| Short Title: | Safety, reactogenicity and immunogenicity of CV7202 in healthy adult subjects |
| Rationale: | The objectives of this phase I trial are to assess the safety and reactogenicity of CV7202 in the context of immune responses to rabies virus glycoprotein (RABV-G) in order to select the optimal dose and number of doses. The dose range selected is intended to provide data for defining the optimal dosage of CV7202 to be tested in subsequent clinical trials. |
| Sponsor: | CureVac AG [name] [name] Germany |
| Coordinating/Principal Investigator: | |

Trial Objectives and Endpoints:

| Objectives | Endpoints |
|--|--|
| Primary | |
| 
To assess the safety and reactogenicity profile of CV7202 administered intramuscularly (i.m.) to healthy adults (18–40 years old), as a range of doses (1, 2 and 5 µg) in one- or two-dose regimens. | 
The percentages of subjects with, and the frequencies and intensities of solicited local adverse events (AEs) reported on the day of vaccination and the 7 subsequent days (Days 1–8). |
| | 
The percentages of subjects with, and the frequencies, intensities and relationship to vaccination, of solicited systemic AEs reported on the day of vaccination and the 7 subsequent days (Days 1–8). |
| | 
The duration (in days) of solicited local AEs, of solicited systemic AEs and of the individual solicited AEs. |

| | |

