^d Second vaccination of CV7202 will be given only to 8 subjects in Groups 3 and 4 (i.e. Groups 3a and 4a).

^e Physical examination and vital signs must be performed/analyzed by a qualified healthcare professional.

^f Vital signs to be checked: body temperature, pulse, blood pressure. Vital signs will be measured pre- and post-vaccination prior to discharge. Subjects will be observed for 4 hours following each vaccination; vital signs must be within normal or clinically non-relevant abnormal ranges or have returned to pre-vaccination values for the subject to be discharged from the phase I Unit.

^g All vaccinated subjects will undergo vaccination site reactogenicity assessment at 1 hour post-vaccination on the day of vaccination (Day 1, Day 8 and Day 29) and 1 or 2 days after each vaccination (Day 2 or 3, Day 10 and Day 30 or 31). Note that Days 3 and 31 were planned in the original protocol and only apply to subjects in Groups 1 and 2 who were already enrolled and vaccinated before this protocol amendment was issued. Local reactions (injection site pain, redness, swelling and itching) will be assessed on an intensity scale of absent, mild, moderate and severe.

^h Solicited and unsolicited AE diaries. Solicited AEs occurring on the day of vaccination (Day 1, Day 8 and Day 29) and for the following 7 days will be recorded by the subject on the diary card. The diary card will be reviewed on Day 2 or 3, 8, 10, 15, 29, 30 or 31, 36, 43 and 57. Unsolicited AEs occurring on the day of vaccination (Day 1, Day 8 and Day 29) and for the following 28 days will be recorded by the subject on the diary card.

ⁱ The VNT serum sample is intended as the baseline value and must be taken before vaccination on Day 1 and Day 29.

^j Hematology (complete blood count, including differential and platelets), biochemistry.

^k Coagulation (activated partial thromboplastin time [aPTT]) and prothrombin time/international normalized ratio (INR) will be performed at the following time points: Screening, Day 1, Day 2 or 3 and Day 30 or 31.

^l In the first 5 subjects in Group 2 and all subjects in Groups 3 and 4. 60 ml for the baseline (Day 1) time point, 40 ml for subsequent blood draws.

^m At each study visit/contact preceding Month 18, SAE and MAAEs considered as related to study vaccination were collected as part of all SAEs and MAAEs.

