9.4.9 Visit 8 (Vaccination Dose 2 CV7202* or Dose 3 Rabipur®, Day 29)

The following procedures will be performed during Visit 8:

- Review of criteria for vaccine delay (for Groups 1, 3a and 4a section 6.3).
- Urine pregnancy test for female subjects of childbearing potential.
- Physical examination (including weight and general condition) and vital signs check (body temperature, pulse, blood pressure).
- Blood draw for:
 - Safety laboratory (~9 ml).
 - Immunogenicity – VNTs (~18 ml), IgM/IgG/IgA (~6 ml) and immune receptor sequencing (~5 ml) in all subjects; cytokine assessment (~6 ml at pre-vaccination and ~6 ml at 4 hours post-vaccination [CV7202 groups only]) and transcriptome profiling (~10 ml at pre-vaccination [CV7202 groups only]) in subjects from Groups 3a and 4a who received a second dose of CV7202.

* The second dose will be administered to 8 subjects of each group (Groups 3a to 4a).

- **Vaccination (Dose 2 CV7202 or Dose 3 Rabipur®).**
- Post-injection vaccination site reactogenicity assessment after 1 hour for all subjects who received a vaccine. Note that all subjects need to remain at the site for 4 hours after vaccination for safety monitoring. Vital signs will be then re-checked and have to be within normal ranges or have returned to pre-vaccination levels for the subject to be discharged.
- Diary review and collection for unsolicited AEs occurring up to Day 29 (Dose 1 CV7202 and Rabipur®) and up to Day 36 (Dose 2 Rabipur®).
- Subjects will be issued with diary cards to record solicited AEs occurring on the day of vaccination with Dose 2 CV7202 or Dose 3 Rabipur® and the following 7 days. Unsolicited AEs occurring on the day of vaccination and for the following 28 days will also be recorded by the subject on the diary card.
- Safety assessments (solicited AEs, unsolicited AEs, SAEs, intercurrent medical conditions, AEs leading to trial or vaccine withdrawal, AESIs and MAAEs, concomitant medications and vaccinations).

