6.1 Baseline Values

Unless otherwise noted, baseline is defined as the last nonmissing value recorded prior to the first administration of the trial product. Unscheduled visits will be used for the determination of baseline values, when applicable.

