6.2 Adjustments for Covariates

Not applicable

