10.2 Secondary Immunogenicity Analysis

The number and percentage of subjects with Rabies Specific serum VNTs ≥ 0.5 IU/ml will be determined for each visit and displayed by vaccination group and dose regimen including 95% exact confidence limits. The percentages will be based on subjects providing data for the respective visit.

For evaluation of values below the limit of quantification (=BLQ values) for tables and figures, the following conventions will be made:

- Values <0.1 are identified as BLQ values.
- All concentration values marked as BLQ will be set to $0.5 * \text{LLOQ}$ (= 0.1 IU/ml) = 0.05 IU/ml
- Missing post-dose values will not be replaced.

Absolute (raw untransformed) serum VNT values will be summarized for each visit by vaccination group and dose regimen.

Serum VNT values will be log-transformed and the mean, SD and 95% confidence interval of the log-transformed values will be calculated. The serum GMTs (= antilog mean of log-transformed data) and the corresponding 95% confidence intervals for the GMTs (=antilog lower and upper 95% confidence bound of log-transformed data) as well as geometric SD, median, minimum and maximum will be tabulated by vaccination group and dose regimen for baseline and each postbaseline visit.

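### The Day 29 pre-dose VNT value is not used as the reference for Dose 2, so the effect of a second dose is read by eye from marginal GMTs of non-randomised groups of 8

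*Protocol*

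**What the plan says.** **Sampling.** Protocol Table 2.1, note i: "The VNT serum sample is intended as the baseline value and must be taken before vaccination on Day 1 and Day 29". Protocol 9.4.9 (Visit 8, Day 29) draws "VNTs (~18 ml), IgM/IgG/IgA (~6 ml) and immune receptor sequencing (~5 ml) in all subjects". Both the one-dose and the two-dose halves of Groups 3 and 4 therefore have a Day 29 titre from before their treatment differs.

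**Baseline for analysis.** Protocol 10.3.6: "Baseline is defined as Day 1 (Visit 3; before vaccination" and no other baseline is named. SAP 6.1, which applies unless a section states otherwise: "baseline is defined as the last nonmissing value recorded prior to the first administration of the trial product". The SAP section headed "Adjustments for Covariates" (6.2) is marked as not applicable.

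**VNT analysis.** SAP 10.2 gives the percentage at or above 0.5 IU/ml at each visit, then "Absolute (raw untransformed) serum VNT values will be summarized for each visit by vaccination group and dose regimen", then GMTs with 95% CIs and geometric SDs, which "will be tabulated by vaccination group and dose regimen for baseline and each postbaseline visit". Shell 14.2.1.4 carries Day 29 as one visit row among the others for 1x1, 2x1, 1x2 and 2x2 µg. No fold rise and no GMT ratio is specified.

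**Purpose and allocation.** The synopsis rationale says safety is assessed alongside immune responses "in order to select the optimal dose and number of doses". Protocol 8.5 says the trial is not randomised, with 8 two-dose and 8 one-dose subjects per dose level. SAP 7 says second doses were given sequentially at the sites and that all analyses follow the regimen received.

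**The concern.** The trial is meant to inform the number of doses, and within each dose level only the comparison of the two halves bears on that. Up to Day 29 both halves had the same single dose, so the Day 29 titre is the last immune measurement before they diverge. A gap between the halves at that point reflects different responses to Dose 1, whether by chance or selection. If it is ignored, it carries forward into the apparent benefit of Dose 2.

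Selection is possible. Protocol 5.1.2 withholds the second dose after certain reactions to the first, and because analysis follows the regimen received, a subject barred for that reason would be counted in the one-dose column.

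The other loss is the rise within each subject after Dose 2. Its estimate can be read off as a ratio of two printed GMTs, but its interval cannot.

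**Working it through.** **The plan's own figures.** There is no power, precision or SD figure to reproduce, because no formal sample size was calculated. The counts agree with Table 8.1: 10 + 10 + 16 + 16 = 52 subjects, 10 + 16 + 16 = 42 on CV7202, and 8 + 8 = 16 second doses.

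**Inputs.** n = 8 per regimen at each dose level (Protocol 8.5). The log10 SD, s, and the correlation r between the Day 29 and later log titres are not in the documents. I assume s = 0.5 (range 0.3 to 0.8), equal at both visits, and r from 0.3 to 0.9. The adjusted formula also assumes one common slope for both regimens.

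**Formulas**, as the half-width of the 95% CI on the log10 scale, then raised as a power of 10:

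- Unadjusted 2-dose/1-dose GMT ratio: t(14) × s × √(2/8). At s = 0.5: 2.145 × 0.5 × 0.5 = 0.536, which is ×/÷3.44.
- Ratio adjusted for Day 29 (approximate): t(13) × s × √(1 − r²) × √(2/8) × √(1 + 1/12). At s = 0.5, r = 0.7: 2.160 × 0.5 × 0.714 × 0.5 × 1.041 = 0.401, which is ×/÷2.52.
- Paired fold rise from Day 29 in one group of 8: t(7) × s × √(2(1 − r)) / √8. At s = 0.5, r = 0.7: 2.365 × 0.5 × 0.775 / 2.828 = 0.324, which is ×/÷2.11.

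| 95% CI factor | r = 0.3 | r = 0.5 | r = 0.7 | r = 0.9 |
|---|---|---|---|---|
| Adjusted ratio, s = 0.3 (unadjusted 2.10) | 2.10 | 1.96 | 1.74 | 1.40 |
| Adjusted ratio, s = 0.5 (unadjusted 3.44) | 3.44 | 3.07 | 2.52 | 1.76 |
| Adjusted ratio, s = 0.8 (unadjusted 7.21) | 7.21 | 6.01 | 4.39 | 2.47 |
| Paired fold rise, s = 0.5 | 3.12 | 2.62 | 2.11 | 1.54 |

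**Why the printed intervals do not suffice.** The variance of a paired mean change is (s₁² + s₂² − 2·r·s₁·s₂)/8. The tables print each SD but not r. At s = 0.5 the interval factor could lie anywhere from 3.12 to 1.54 over the assumed range of r. The unadjusted ratio between regimens can be worked out from the printed summaries, since the two groups are separate subjects. The paired and adjusted quantities cannot.

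**Size of a Day 29 gap.** Even under random allocation, the chance that two groups of 8 differ at least 2-fold in Day 29 GMT is 2 × [1 − Φ(0.301/(s × √(2/8)))]: 4.5% at s = 0.3, 23% at s = 0.5 and 45% at s = 0.8. On average a 2-fold gap carries into the later unadjusted ratio as 2^r: 1.41-fold at r = 0.5, 1.62 at 0.7 and 1.87 at 0.9.

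**Values below quantification.** SAP 10.2 sets titres under 0.1 IU/ml to 0.05. A subject below the limit on Day 29 who later reaches 0.5 IU/ml is credited with 0.5/0.05 = 10-fold, although all that is known is a rise of more than 0.5/0.1 = 5-fold.

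**Cytokines.** SAP 10.3.3 summarises change from baseline and names no other reference, so the SAP 6.1 definition applies. Protocol 9.4.9 draws a fresh pre-vaccination cytokine sample on Day 29 in Groups 3a and 4a, yet change after Dose 2 would refer to Day 1. Here the baseline rule directly alters a planned output.

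**The case against.** Three stronger readings are tempting, and the documents do not support them.

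- *That the Day 1 baseline definition causes the gap.* For VNT, SAP 10.2 computes no change from any baseline, Day 1 included. Redefining baseline alone would alter no VNT table. Note i also sits in the schedule of activities and can be read simply as a sampling instruction.
- *That the Day 29 value goes unused.* It has its own row by regimen in 14.2.1.2 and 14.2.1.4, beside Days 36, 43 and 57, and listing 16.2.6.1 prints each subject's titres. A careful reader can see a gap at Day 29 and, from the listing, derive the paired changes. What is missing is a pre-specified summary with an interval.
- *That the Day 29 titre captures exactly the imbalance to be removed.* It captures differences in antibody response to Dose 1. Site, calendar time and reactogenicity are not contained in one titre.

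It is also fair to say that the trial is descriptive, that the VNT endpoints are per-group percentages and GMTs, that no decision rule rests on VNT, and that no contrast between regimens is an endpoint. This limits the weight of the point, but a fold change with a CI is itself descriptive and SAP 10.2 already prints CIs.

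Two further limits stand. At doses of 1 and 2 µg many Day 29 titres could be below quantification, leaving little to adjust for. And SAP 10 refers details of immunogenicity data analysis and reporting to an immunomonitoring analysis plan that is not among the documents, so the absence is shown only for the protocol and SAP.

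**Conclusion.** The point holds as a cheap improvement to estimation and reporting, not as an error in the plan and not as a sample-size fault. The trial collects the right pre-dose value in everyone and then gives it no role beyond a visit row, although the number of doses is a stated question and the regimen groups are small, non-randomised, filled sequentially and analysed as received.

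At an assumed log10 SD of 0.5, adjustment moves the CI factor for the regimen ratio from 3.4 to between 3.4 and 1.8, depending on the correlation. There is no precision gain at 0.3 and a clear one from 0.7 upward. These figures rest on assumed SDs and correlations, roughly normal log titres, and Day 29 values that are mostly quantifiable. Adjustment reduces imbalance in the response to Dose 1; it does not turn the regimen comparison into a randomised one.

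**What to change.** - **SAP 6.1 and 10.2:** keep Day 1 as baseline for Dose 1 and name the Visit 8 pre-dose value as the reference for summaries after Dose 2. Reconcile note i of Table 2.1 with Protocol 10.3.6.
- **Shell 14.2.1.4:** for 1x1, 2x1, 1x2 and 2x2, add the geometric mean fold change from Day 29 to Days 36, 43 and 57 with 95% CI, and the number below quantification on Day 29.
- **Exploratory row for each dose level:** the 2-dose/1-dose GMT ratio at Days 43 and 57 from log10 VNT on regimen plus Day 29 log10 VNT, provided Day 29 is not mostly below quantification. Label it non-randomised.
- **SAP 10.3.3:** in Groups 3a and 4a, refer cytokine change after Dose 2 to the Day 29 pre-vaccination sample.
- **Optional:** the fold change after Rabipur Dose 3. The objective concerns the three-dose regimen as a whole, so this is not needed.

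The cost is SAP wording and a few rows, with no new samples. Fold changes remain hard to read where Day 29 is below quantification. The SAP is dated 24 February 2022, and SAP 6.4 reports an interim analysis of immunogenicity through Day 57 as already done. Anything added after the SAP is final must carry the post hoc label that SAP 6 requires.
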